6 STUDY PROCEDURES

6.1 Study Schedule

All required study visits and procedures are outlined in [Appendix 1](#).

6.2 Study Assessments

The safety of ARCT-021 will be monitored in an ongoing fashion during the study by the Sponsor Medical Monitor (or designee) and Principal Investigator.

All subjects will have blood samples taken at intervals throughout the study for assessment of immunogenicity as detailed in [Appendix 1](#). [Appendix 2](#) shows a list of analytes required for the study.

Subjects who do not receive ARCT-021 in this study will not have any further laboratory safety evaluations performed in this study.

For subjects receiving ARCT-021 in this study, blood and urine samples will be collected for safety evaluations up to 28 days after the last injection of ARCT-021 ([Appendix 1](#)). Additionally, local and systemic solicited and unsolicited AEs will be recorded daily by the subject in a symptom diary as described in Section [6.2.1](#).

In both subjects who do not receive ARCT-021 and in subjects who do receive ARCT-021 in this study, Serious Adverse Events (SAE), New Onset of Chronic Disease (NOCD), Clinical Events of Special Interest (CESI) and Medically Attended AE (MAAE) will be collected for the duration of the study.

Additionally, subjects that receive ARCT-021 in this study will have local and systemic solicited AE recorded for 7 days (and up to 14 days if still persisting at 7 days) after injection and non-serious unsolicited AE recorded for 28 days after injection.

6.2.1 Adverse Event Assessments

See also Section [9.4](#) and [Appendix 1](#).

For those subjects who receive a dose of ARCT-021 in this study:

Local and systemic solicited and unsolicited AEs will be recorded daily by the subject in a symptom diary for at least 7 days post injection and up to 14 days post injection if any events are persisting at 7 days. Subjects will record their temperature daily in the symptom diary during these 7 days. Additionally, any injection site erythema or swelling will be measured in the longest dimension and recorded in the symptom diary.

Unsolicited adverse events will be collected at each study visit from post injection on Day 1 throughout the participation of the subject in the study; however, after a subject reaches Day 29 of study participation only the unsolicited AEs defined as MAAEs, SAEs, CESIs, NOCDs will be summarized. Unsolicited adverse events will be determined from reporting of these events in the diary card, review of clinical laboratory values, performance of physical exam, and interview of the subject.

The symptom diaries will be reviewed by site staff at the Day 8 (and Day 15 if subject completing diary for an additional 7 days) visit for the first injection and at the Day 36 (and Day 43 if subject completing diary for an additional 7 days) visit for the second injection. Subjects will be specifically questioned about injection site and systemic (fever, fatigue, headache, chills, nausea, vomiting, diarrhoea, new or worsened myalgia, and new or worsened arthralgia) at these visits.

Should a solicited AE persist beyond 14 days post injection (past Day 15 for the first injection or Day 43, if second injection), this will be followed by interview and/or physical examinations at follow-up visits until resolution or stabilization.

Study site staff will enter the temperature and erythema/swelling dimension measurements recorded in the symptom diary into the EDC. Subjects grading of reactogenic events, as recorded in the symptom diary, will be entered in the EDC without change. Any unsolicited events recorded by the subject in the symptom diary will be entered verbatim into the EDC.

Any recorded temperature $\geq 38^{\circ}\text{Celsius}$ ($\geq 100.4^{\circ}\text{ Fahrenheit}$) or injection site erythema/swelling $\geq 25\text{mm}$ in size will be reported as an adverse event and graded according to Toxicity Grading Scale for Healthy Adult and Adolescent Volunteers Enrolled in Preventive Vaccine Clinical Trials, Sept 2007.

Solicited events with onset within 7 days of injection will be considered related.

Symptom diaries will be collected at the Day 8 or 15 (depending on completion status) visits for the first injection and 36 or 43 visits for the second injection and will serve as source documents.

For those subjects who received ARCT-021 in the Parent Study:

At Screening, SAEs, NOCDs, CESIs and MAAEs occurring between completion of the Parent Study and the Screening visit for this study will be solicited and recorded in the EDC to ensure continuity of safety follow-up from the Parent Study to this study. Events that occurred prior to dosing in this study will be recorded as medical history.

For subjects who received ARCT-021 in either the Parent Study or this study:

SAEs, NOCDs, CESIs, and MAAEs will be collected for all enrolled subjects for the duration of the study until the Final Visit (Day 365 or Day 281 if vaccinated or not vaccinated with ARCT-021 in this study) or Early Termination visit (if applicable).

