9.4.1 Serious Adverse Events

In the interest of subject safety, and in order to fulfill regulatory requirements, all SAEs (regardless of their relationship to Study Drug) should be reported to the Sponsor or designee within 24 hours of the Study Center's first knowledge of the event.

For subjects that received ARCT-021 in the parent study, the collection of SAE will begin at the Screening visit, when SAE (and MAAE) occurring since completion of the Parent Study will be solicited to ensure continuity of safety follow-up from the Parent Study to this study, and stop at the end of the subject's follow-up period which is defined as the subject's last protocol-specified study visit.

For subjects who receive ARCT-021 in this study and who did not receive ARCT-021 in the Parent Study, the collection of SAEs will begin after the subject has received ARCT-021 and stop at the end of the subject's follow-up period. SAEs that occur prior to administration of ARCT-021, including those that occurred between leaving the Parent Study and dosing in this Study, will be recorded as medical history.

SAEs considered to be related or possibly related to Study Drug and any deaths will continue to be reported for 30 days after the subjects last study visit. SAEs will be reported within the electronic data capture system (EDC) whenever possible. If the EDC is not available, the SAE can be initially reported using a paper Initial Serious Adverse Event Form, which should be faxed or emailed to the Sponsor or designee. The SAE reporting instructions, including the fax number and email address for submitting paper forms can be found in the Investigator site file for the study. If the Investigator is reporting by telephone, it is important to speak to someone in person versus leaving a message.

Detailed information should be actively sought and included on Follow-Up Serious Adverse Event Forms as soon as additional information becomes available. All SAEs will be followed until resolution. SAEs that remain ongoing past the subject's last protocol-specified follow-up visit will be evaluated by the Investigator and Sponsor. If the Investigator and Sponsor agree the subject's condition is unlikely to resolve, the Investigator and Sponsor will determine the follow-up requirement.

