9.4.2 Medically Attended Adverse Events

For subjects that received ARCT-021 in the parent study, the collection of MAAE will begin at the Screening visit, when MAAE (and SAE) occurring since completion of the Parent Study will be solicited to ensure continuity of safety follow-up from the Parent Study to this study, and stop at the end of the subject's follow-up period which is defined as the subject's last protocol-specified study visit.

For subjects who receive ARCT-021 in this study and who did not receive ARCT-021 in the Parent Study, the collection of MAAEs will begin after the subject has received ARCT-021 and stop at the end of the subject's follow-up period. MAAEs that occur prior to administration of ARCT-021, including those that occurred between leaving the Parent Study and dosing in this Study will be recorded as medical history.

MAAEs that also fulfil the criteria of an SAE should be reported to the Sponsor or designee within 24 hours of the Study Center's first knowledge of the event (Section 9.4.1).

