9.4.3 Non-Serious Adverse Events

For subjects who receive ARCT-021 in this study and who did not receive ARCT-021 in the Parent Study, the recording of non-serious AEs will begin after the subject has received ARCT-021 and will stop 28 days after the last dose of ARCT-021, with the exception of ongoing adverse events that worsen in severity and/or become serious, which will continue to be recorded. AEs that occur prior to administration of ARCT-021, including those that occurred between leaving the Parent Study and dosing in this Study will be recorded as medical history.

For subjects who receive ARCT-021 in this study and who also received ARCT-021 in the Parent Study, the recording of non-serious AEs will begin from the time the subject received ARCT-021 in the Parent Study and will stop 28 days after the dose of ARCT-021 in this study, with the exception of ongoing adverse events that worsen in severity and/or become serious, which will continue to be recorded. Any AEs that occurred between leaving the Parent Study and entering this study will be recorded as AEs.

For subjects who do not receive ARCT-021 in this study, only medically attended non-serious events will be recorded as described above (Section 9.4.2). The Investigator will monitor each subject closely and record all observed or volunteered AEs in the EDC.

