14 APPENDICES

APPENDIX 1: SCHEDULE OF ASSESSMENTS

Appendix 1: Schedule of Assessments

1. Screening

Subjects who Received Placebo or a Single Injection of ARCT-021 in Parent Study

Study Week/Day	D -28 to D -1
Visit Window (Days)	0
Informed Consent	X
Inclusion/Exclusion	X
Body Weight	X
Physical Exam ¹	X
Vital Signs ²	X
Pregnancy Test ³	X
Chemistry Panel	X
Hematology	X
Coagulation	X
HbA1c	X
Urinalysis ⁴	X
Immunogenicity ⁵	X
Drug/Alcohol Screen ⁶	X
SAE, CESI, NOCD and MAAE ⁷	X
Concomitant Medications and Procedures ⁸	X
SARS-CoV-2 questioning ⁹	X

1 Full physical exam

2 BP, HR, RR, temp

3 Women who are not surgically sterile or post-menopausal. Dipstick acceptable

4 Dipstick test per local procedures. If abnormal send sample to laboratory for microscopy.

5 This is only PRNT50 for the screening visit

6 Urine test.

7 SAE, CESI, NOCD and MAAE that occurred since completion of the Parent Study and screening for this study will be recorded. For subjects that received ARCT-021 in the Parent Study, these will be entered as SAE/CESI/MAAE in the EDC. For subjects that received placebo in the Parent Study these will be recorded as medical history.

8 Concomitant medications and procedures since completion of the Parent Study and screening for this study will be recorded for all subjects.

9 Subjects will be questioned about symptoms of COVID-19 and exposure to confirmed COVID-19 or confirmed SARS-CoV-2 infection cases amongst household contacts, friends, work contacts and other contacts.

Subjects who Received Two Injections of ARCT-021 in Parent Study

Study Week/Day	D -28 to D -1
Visit Window (Days)	0
Informed Consent	X
Inclusion/Exclusion	X
Body Weight	X
Physical Exam ¹	X
Vital Signs ²	X
SAE, CESI, NOCD and MAAE ³	X
Concomitant Medications and Procedures ⁴	X
SARS-CoV-2 questioning ⁵	X

- 1 Full physical exam (assessment of heart, lungs, abdomen, eyes, ears, nose and throat, head and neck, musculoskeletal, lymphatic, injection site, dermatologic, neurologic, extremities)
- 2 BP, HR, RR, temp
- 3 SAE, CESI, NOCD and MAAE that occurred since completion of the Parent Study and screening for this study will be recorded
- 4 Concomitant medications and procedures since completion of the Parent Study and screening for this study will be recorded
- 5 Subjects will be questioned about symptoms of COVID-19 and exposure to confirmed COVID-19 or confirmed SARS-CoV-2 infection cases amongst household contacts, friends, work contacts and other contacts.

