8.1.9.1 Unsolicited Adverse Event Summaries

All unsolicited AEs (serious and non-serious) occurring after exiting Parent study and after administration of first dose of study vaccine (in this study or parent study as applicable) and before the End of Study or Off-study vaccination, regardless of relationship to study vaccine, will be included and classified by system organ class (SOC) and preferred term (PT) using the Medical Dictionary for Regulatory Activities (MedDRA).

- For Cohort 1a, AE occurring from the time of exiting the Parent Study up to receipt of Study Vaccine on Day 1 will be regarded as medical history. All unsolicited events, including SAEs, MAAEs, and NOCD are collected up to 28 days after receipt of study vaccine and only SAEs, MAAEs, and NOCD are collected beyond 28 days after receipt of study vaccine.
- For Cohort 1b, SAEs, MAAEs, and NOCD occurring from the time of exiting the Parent Study up to receipt of study vaccine on Day 1 will be regarded as treatment emergent but will be presented separately (as 'Pre-Study TEAEs') to TEAEs occurring after receipt of vaccine. All unsolicited events, including SAEs, MAAEs, and NOCD are collected up to 28 days after receipt of study vaccine in Study ARCT-021-02 but only SAEs, MAAEs, and NOCD are collected beyond 28 days after receipt of study vaccine.
- For Cohort 2 only SAEs, MAAEs, and NOCD are collected in Study ARCT-021-02 as no further study vaccine is administered in this study. All events reported from the time of exiting the Parent Study up to the data cut point for this interim analysis are regarded as treatment emergent and will be presented merged for the purposes of tabulation.

Solicited systemic and local adverse events will not be included in the unsolicited AE summaries, unless the solicited AE has onset >7 days after administration of Study vaccine or the solicited event is serious or medically attended.

Unsolicited AEs that appear within the Toxicity Grading Scale for Healthy Adult and Adolescent Volunteers Enrolled in Preventive Vaccine Clinical Trials, Sept 2007 will have been entered in the EDC with a numerical Grade (1 to 4). Unsolicited TEAEs that are not contained within this scale will have been graded as mild/moderate/severe. For the purposes of tabulation of unsolicited AEs, events will be presented as mild/moderate/severe, whereby the CRF-designated Grade 1 = mild, Grade 2 = moderate and \geq Grade 3 = severe.

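### Protocol 6.2.1 files between-study events as medical history for Cohort 1b, against Protocol 9.4 to 9.4.3, Appendix 1 and the SAP, so the Cohort 1b pre-study safety summaries may be under-counted

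*Protocol*

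**What the plan says.** The paragraph in Protocol 6.2.1 opens "For those subjects who received ARCT-021 in the Parent Study". It asks for SAEs, NOCDs, CESIs and MAAEs between parent-study completion and screening, which "will be solicited and recorded in the EDC to ensure continuity of safety follow-up from the Parent Study to this study". The next sentence gives the classification: "Events that occurred prior to dosing in this study will be recorded as medical history".

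Other parts of the protocol give a different rule for the same people:

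- Section 9.4 keeps medical history for conditions present before the first ARCT-021 injection.
- Section 9.4.1: "For subjects that received ARCT-021 in the parent study, the collection of SAE will begin at the Screening visit", looking back to the end of the parent study.
- Section 9.4.2: "For subjects that received ARCT-021 in the parent study, the collection of MAAE will begin at the Screening visit", with the same look-back.
- Section 9.4.3, for people dosed in both studies: "Any AEs that occurred between leaving the Parent Study and entering this study will be recorded as AEs".
- Appendix 1, screening footnote 7: "For subjects that received ARCT-021 in the Parent Study, these will be entered as SAE/CESI/MAAE in the EDC". The footnote keeps medical history for placebo recipients.

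The SAP follows this second rule. Sections 4.4 and 5 handle the gap events of Cohorts 1b and 2 as adverse events, and 8.1.1 defines them as treatment emergent. Section 8.1.9.1 says that Cohort 1b SAEs, MAAEs and NOCDs from the gap "will be regarded as treatment emergent but will be presented separately", under the label Pre-Study TEAEs. Section 8 lists a pre-study window for Cohort 1b among the primary safety endpoints.

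**The concern.** The form on which an event is entered decides which table it reaches. An event entered only as medical history goes to the summary in SAP 6.3. It would not be expected in the treatment-emergent tables, the listings, or the individual narratives that SAP 8.1.4 to 8.1.6 promise for SAEs, MAAEs and NOCDs.

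For Cohort 1b, the gap is the later follow-up after a first ARCT-021 dose and before a second. The continuity sentence in 6.2.1 exists to capture late events in that period. If the site followed the sentence after it, the pre-study count for Cohort 1b would reflect a filing rule as well as what happened to the participants. A low or zero count could then be read as reassurance that it does not give.

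**Working it through.** The plan states no figure for this point, so the check is a comparison of texts plus one piece of arithmetic on nominal days.

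**Step 1: whom the sentence reaches.** It needs ARCT-021 in the parent study (the paragraph's opening) and a dose in this study (its own wording).

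| Group | ARCT-021 in parent study | Dosed in this study | Does the 6.2.1 sentence apply? |
|---|---|---|---|
| Cohort 1a | No (placebo) | Yes | No, outside the paragraph |
| Cohort 1b | Yes | Yes | Yes |
| Cohort 2 | Yes | No | No dose to be prior to |

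**Step 2: how each place classifies a Cohort 1b gap event.**

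| Place | Classification |
|---|---|
| Protocol 6.2.1 | Medical history |
| Protocol 9.4 | Not history, since the first injection was in the parent study (unless pre-existing before it) |
| Protocol 9.4.1 | SAE |
| Protocol 9.4.2 | MAAE |
| Protocol 9.4.3 | AE |
| Protocol Appendix 1, footnote 7 (repeated in SAP Appendix A) | SAE/CESI/MAAE |
| SAP 4.4, 5 | AE, shown separately |
| SAP 8.1.1, 8.1.9.1 | TEAE, pre-study |

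Sections 9.4.1 and 9.4.2 are the most direct conflicts for SAEs and MAAEs. Section 9.4.3 covers non-serious events.

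**Step 3: could the sentence be the governing rule?** The medical history rule in 9.4.1, 9.4.2 and footnote 7 is for people with no ARCT-021 in the parent study. The 6.2.1 sentence reads like that rule placed under the wrong group. The summary of changes lists both 6.2.1 and 9.4.3 as clarified in the same amendment, so date does not decide between them. SAP 6.3 sends events before the first injection of study vaccine to medical history. SAP 8.1.9.1 takes the first dose as the one in this study or the parent study, as applicable. For Cohort 1b that is the parent-study dose, so 6.3 does not support 6.2.1.

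**Step 4: length of the window.** SAP 5.3.2 gives 57 days in the parent study for single-dose cohorts and a nominal 90 days to Day 1 here. 57 + 90 = 147, which matches the SAP's own figure. The gap is 90/147 = 61% of the nominal time from first dose to Day 1 of this study.

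**Step 5: number of events.** This would be the gap event count in Cohort 1b times the share filed as history. The documents give neither factor, nor the size of Cohort 1b, so no estimate is possible.

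**The case against.** The strongest reply is that one stray sentence stands against a consistent rule, and that the SAP reports what was done. Section 6.2.1 itself points to 9.4 and Appendix 1. SAP 8.1 says, in the past tense, that between-study MAAE, NOCD and CESI events in Cohorts 1b and 2 were recorded in this study's eCRF and will be included. SAP 5 says that Cohort 1b events before Day 1 are handled as adverse events, and its instruction to enter earlier events as medical history sits under Cohort 1a. SAEs must also reach the sponsor within 24 hours under 9.4.1, and misfiled events would still appear in the medical history table.

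Most of this stands, and it lowers the practical risk. It does not close the point, for three reasons:

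- SAP 8.1 does not name SAEs in that statement, although SAP 8 and 8.1.9.1 include them in the pre-study window.
- Being in the eCRF does not show which form was used. SAP 4.4 says that Cohort 1a history is captured in the EDC as well.
- SAP 5.1 says that data are pulled while source verification and query resolution are still ongoing, so routine cleaning cannot be assumed to have caught misfiled events.

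A reader might also infer that 9.4.3 should be narrowed to SAEs, MAAEs, NOCDs and CESIs. The documents do not require that. Section 6.2.1 says what is solicited and 9.4.3 what is recorded, and narrowing would discard non-serious events that the protocol now keeps.

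**Conclusion.** The 6.2.1 sentence is wrong as written for Cohort 1b and should be corrected. If the site followed it, SAEs, MAAEs and NOCDs from the nominal 90-day gap would be misfiled, and both the Pre-Study TEAEs presentation and the SAP section 8 pre-study window would be under-counted.

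The size is unknown. A reader might infer that every Cohort 1b gap event is missing from the safety tables, or that the SAP could do nothing about it. The documents support neither reading. Total misfiling is only the ceiling of what could happen, and SAP 5 and 8.1 indicate that the events were meant to be, and largely were, handled as adverse events. Misfiled events would be recorded and recoverable. Because the SAP shows the gap separately, Cohort 1b rates after the dose in this study do not change.

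The conclusion assumes that an event held only as medical history does not feed the adverse event tables. That is the natural reading of SAP 6.3 and 8.1.9.1, but no eCRF or dataset specification is available to confirm it.

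**What to change.** 1. In Protocol 6.2.1, delete the sentence or move it to a line for parent-study placebo recipients, so that it agrees with 9.4 to 9.4.3 and Appendix 1.
2. Before tabulation, query Cohort 1b medical history for onset dates between parent-study exit and Day 1 of this study. Move qualifying SAEs, MAAEs and NOCDs to the adverse event form, and report how many were moved.
3. In SAP 8.1, add SAEs to the statement on what was recorded and name the form used.
4. Reconcile the open-ended scope of 9.4.3 with the solicited list in 6.2.1 and Appendix 1, stating which non-serious gap events are expected. Section 9.4.3 need not be narrowed.

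The cost is a few sentences of text and one data query at a single site. No analysis method or sample size changes.

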6.2.2 Blood Pressure Recording

The following procedure should be followed for recording of blood pressure (note if an automated BP recording device is used then only the first 3 points need to be observed):

- Subject should be seated comfortably or semi-recumbent, with back supported, legs uncrossed, and upper arm bared.

- The subject's arm should be supported at heart level.
- Cuff bladder should encircle 80 percent or more of the subject's arm circumference.
- Neither the subject nor the person taking the measurement should talk during the procedure.
- The cuff should be deflated at 2 to 3 mm per second.
- The first and last audible sounds should be recorded as systolic and diastolic pressure, respectively. Measurements should be given to the nearest 2 mm Hg.

6.2.3 Immunogenicity Assessments

SARS-CoV-2 neutralising antibody titer will be tested using an in vitro plaque reduction neutralisation test (PRNT) and/or pseudovirus neutralization test and/or surrogate virus neutralization test (sVNT) and/or microneutralization test. Testing using other SARS-CoV-2 isolates may also be performed.

Total IgG against the full-length SARS-CoV-2 recombinant spike protein and/or spike protein subunits will be assessed using an immune-Luminex and/or ELISA assay.

T-cell subclass responses will be tested by flow cytometry and ELISPOT assay using peptide pools from SARS CoV-2 spike protein.

